Sample size. Sample size for other analyses was determined using power analysis for hypothesis tests related to the Primary Aim of Study 2, specifically to detect a significant difference between the reduced-nicotine condition and the usual brand condition in the primary endpoints, cigarettes per day (CPD) and urine cotinine, at the end of the trial. Effect size estimates were based on our previous studies of normal nicotine cigarettes (NNC) and VLNC use in disadvantaged women of childbearing age and estimates of CPD in our completed study on smoking topography in pregnant women and women of childbearing age. In that study, pregnant women smoked an average of 12.1 CPD, while preliminary data from our trial of women of childbearing age suggest a decrease of 5 CPD in women smoking VLNC compared to those smoking NNC. A sample size of 45 completers per condition will provide 80% power to detect statistically significant differences in smoking rate.

Potential Risks of Participation

- 1) Smoking Cigarettes: All cigarettes are detrimental to a person's health and can lead to significant medical problems including:
 - a. Risk to Fetus: Miscarriage, preterm delivery, stillbirth, low birth weight, problems with the placenta, birth defects such as cleft palate, sudden infant death syndrome (SIDS), and early childhood behavioral problems.
 - b. Cardiovascular Diseases: Coronary heart disease, heart attack, stroke, peripheral vascular disease, reduced blood circulation, abdominal aortic aneurysm
 - c. Respiratory Diseases: Emphysema, bronchitis, and chronic airway obstruction
 - d. Cancers: Cancer of the lung, bladder, cervix, esophagus, kidney, larynx, mouth, pancreas, throat, and stomach; leukemia
 - e. Metabolic Diseases: Type 2 Diabetes

- f. Other Health Risks Associated with Smoking: Including but not limited to infertility, lower bone density in postmenopausal women, and hip fracture in women
 - g. Death
- 2) Smoking Withdrawal: Participants may experience smoking withdrawal symptoms during this study. The symptoms can be uncomfortable but are typically of minimal risk. Smoking withdrawal symptoms include:
 - a. Anger, irritability, frustration
 - b. Anxiousness, nervousness
 - c. Depressed mood or sadness
 - d. Desire or craving to smoke
 - e. Difficulty concentrating
 - f. Increased appetite, hunger or weight gain
 - g. Insomnia, problems sleeping or awakening at night
 - h. Restlessness
 - i. Impatience
 - j. Constipation
 - k. Dizziness
 - l. Coughing

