The sponsors (NIDA/FDA) as well as the Institutional Review Board and regulatory authorities could be granted direct access to original medical and research records for verification of clinical trial procedures and/or data. If this is required, it will be done under conditions that will protect privacy to the fullest extent possible consistent with laws relating to public disclosure of information and the law-enforcement responsibilities of the agency.

Data Storage:

Data will be stored locally for at least 7 years after study completion at the University of Vermont.

Adverse Events

The research assistant will ask about adverse events at each visit during the study, using a form that assesses the nature, severity, duration, action taken, and outcome of study-related adverse events. AEs will be captured from the time of study consent. Participants will be given contact cards to inform us of events that occur between study contacts. Any AE that remains open will be reviewed and closed at the study completion date (completers, withdrawn, etc.)

All procedures will be monitored to ensure that they conform to the approved protocol. In addition, monitoring will be done of all unforeseen circumstances that might arise and affect safety; of all reports of serious adverse events as defined in 38 CFR 46 (death, new or prolonged hospitalization, persistent or significant disability/incapacity); of other significant adverse events (adverse events that lead to drop out by the participant or termination by the investigator); of unexpected adverse events resulting from the study, and of expected adverse events.

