Any SAE will be brought to the attention of the site PIs as soon as possible and not longer than 24 hours. Any AE or SAE that is both unexpected and related to study participation will be reported to the IRB within 7 days of the event. The IRB will make a determination as to whether additional reporting requirements are needed. IRB actions will be reported to the funding agency by the PIs no less than annually and more frequently as recommended by the local IRB. Any SAEs will be summarized in the yearly Progress Reports to the funding agency, including a review of frequency and severity. All SAEs will be followed through ongoing consultation with the physician caring for the patient until they resolve, result in death, or stabilize and are not expected to improve. The study staff will be in close contact with participants and health care providers throughout the study to monitor for potential unanticipated problems. Any unanticipated problems will be discussed at the weekly research staff meetings and reported as required to the local IRB.

Withdrawal or Monitoring of Participants

For the participant's protection, participants will be withdrawn immediately from the study if any of the following occur:

- 1) Pregnancy complication: Typically includes miscarriage, stillbirth, or preterm delivery.
- 2) Cardiovascular disease (CVD) event: Typically includes MI (heart attack), PTCA (angioplasty/stenting), bypass surgery, stroke, peripheral vascular disease (arterial blockages in arms or legs leading to procedure or surgery). Less common CVD problems would be new cardiac arrhythmias (e.g., new atrial fibrillation) or new valvular disease (e.g., mitral or aortic regurgitation).
- 3) Deep vein thrombosis (DVT)/pulmonary embolism (PE): I.e., blood clots in the venous system.
- 4) Suicide attempt: A participant will be withdrawn if she attempts suicide at any time during participation in the study.
- 5) Psychiatric hospitalization: A participant will be withdrawn if she is hospitalized for psychiatric reasons at any time during participation in the study.

- 6) Expired breath CO increase: A participant will be withdrawn from the study if the average of two consecutive CO readings during the same visit is more than double their Baseline exhaled CO measurement, or greater than 50 ppm at any given time.

The following will be monitored and can lead to the participant being withdrawn by the PI or Licensed Medical Professional:

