### **6.4. Safety Endpoints**

- Adverse events (AEs)
- Serious adverse events (SAEs)
- Birth outcomes
  - Live birth
  - Birth weight
  - Mother's gestational age at delivery
  - Type of nursery admission

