### **8.1. Adverse Events**

Safety data will include the number of adverse events, classified as to category. Categories of events are based on the Medical Dictionary for Regulatory Activities (MedDRA). In addition to the type of event, adverse events will be categorized by severity, whether the adverse event is related to the study products/procedures, and whether the adverse event is expected.

Summary frequencies will be provided based on the overall number of events as well as separately by dose condition. In addition to the number of events of a particular type recorded, the percent of adverse events will be computed with the denominator being the number of participants in the safety population. Thus, the description of events will be reported as events/person. Categorization of the severity of events, relationship to study product/procedures, and expected nature of the event will be also reported as the frequency and percent of participants.

Safety analyses will be reported only to the DSMB and the appropriate Institutional Review Boards, with the exception that any serious adverse event will also be reported to the study sponsor.

Birth outcomes will be reported descriptively.

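### Birth defects are a named fetal risk, but neither the SAE definition nor the SAP birth-outcome list includes them, so nothing ensures that one found at delivery is captured, promptly notified or tabulated by arm

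*Protocol*

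**What the plan says.** **Named risk.** Under Potential Risks of Participation, the protocol's risks to the fetus include "birth defects such as cleft palate".

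**SAE definition.** The protocol's Adverse Events section refers to "serious adverse events as defined in 38 CFR 46 (death, new or prolonged hospitalization, persistent or significant disability/incapacity", and the list ends there. The same section adds monitoring "of unexpected adverse events resulting from the study, and of expected adverse events", with no deadline attached.

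**Reporting rules.** Two time limits follow:
- The site PIs must hear of every SAE within a limit of 24 hours.
- The limit for the IRB does not depend on seriousness: "Any AE or SAE that is both unexpected and related to study participation will be reported to the IRB within 7 days of the event".

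SAEs are also summarized in yearly progress reports to the funder. Under SAP 8.1, they are the one kind of safety result that also goes to the sponsor.

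**Collection window.** Staff ask about adverse events at each visit from consent onward. Events still open are closed at study completion. The call 25 to 35 days after the abstinence session asks about smoking and goes over Medical Event Forms that are still open.

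**Birth outcomes.** Under Birth Outcomes Data, the protocol plans a review of maternal birth records and names no variables. SAP 6.4 names four: live birth, birth weight, gestational age at delivery and "Type of nursery admission". SAP 8 limits reported safety data to adverse events and birth outcomes. SAP 8.1 adds: "Birth outcomes will be reported descriptively".

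**The concern.** Study 2 enrols only pregnant women and assigns half of them to a research cigarette for 12 weeks. Its safety reporting has two channels, adverse events and birth outcomes, and a fetal risk that the protocol itself names has an assured place in neither.

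SAE status decides whether the site PIs hear within 24 hours and whether the event appears in reports to the funder and sponsor. The SAP list decides what is abstracted from the birth record and shown in a table. If both are followed as written, the handling of an anomaly found at delivery depends on when the woman enrolled and on how a staff member chooses to classify the event.

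**Working it through.** The plan states no figure on this point, so there is none to reproduce. The check has three parts.

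**1. The lists side by side**

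| Place | Content | Congenital anomaly? |
|---|---|---|
| Protocol, Potential Risks of Participation | Risks to the fetus | Yes |
| Protocol, Adverse Events | SAE: death, hospitalization, disability/incapacity | No |
| Protocol, Withdrawal or Monitoring of Participants | Pregnancy complications: miscarriage, stillbirth, preterm delivery | No |
| Protocol, Birth Outcomes Data | Record review, variables not named | Not stated |
| SAP 6.4 | Four birth outcomes | No |

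**2. Does adverse-event collection reach delivery?**

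Inputs from the protocol: gestational age at most 25 weeks at enrolment; Baseline 1 within 30 days of screening; Baseline 2 after a further 7 to 21 days; 12 weeks of visits; abstinence session the next day; call 25 to 35 days after that. Term is assumed to be about 37 to 41 weeks. Visit windows of ±3 days are ignored.

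- Screening to Baseline 2: shortest 0 + 7 days = 1.0 week; longest 30 + 21 = 51 days = 7.3 weeks.
- Week 12 visit = gestational age at screening + (1.0 to 7.3) + 12 weeks.
- Call = Week 12 visit + 1 day + 25 to 35 days, that is + 26 to 36 days (3.7 to 5.1 weeks).

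| Gestational age at screening | At Week 12 visit | At call |
|---|---|---|
| 12 weeks | 25.0-31.3 | 28.7-36.4 |
| 20 weeks | 33.0-39.3 | 36.7-44.4 |
| 25 weeks | 38.0-44.3 | 41.7-49.4 |

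A woman screened at 12 weeks has her last scheduled contact before term, even on the slowest schedule. One screened at 25 weeks may still be attending visits when she delivers. Capture through adverse-event questions therefore depends on gestational age at entry. For early enrollees, the birth-record review is the only systematic source after delivery.

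**3. How many cases might arise**

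The protocol's Study 2 Randomization section sets 106 randomized women (90 / 0.85 = 105.9, rounded up), allocated equally, so about 53 per arm. The documents give no anomaly rate; 2% to 5% is an assumption.

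- Both arms: 106 × 0.02 = 2.1; 106 × 0.05 = 5.3. Chance of at least one case: 1 − 0.98^106 = 0.88; 1 − 0.95^106 = 0.996.
- VLNC arm: 53 × 0.02 = 1.1; 53 × 0.05 = 2.7. Chance of at least one case: 1 − 0.98^53 = 0.66; 1 − 0.95^53 = 0.93.

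These figures treat every randomized woman as contributing one birth with an available record, so they are upper figures for the assumed rates.

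**The case against.** The strongest reply is that several routes stay open:
- Expected and unexpected adverse events are both monitored, and participants hold contact cards for events between visits.
- SAP 8.1 tabulates recorded adverse events by MedDRA category, overall and by condition, so an anomaly entered as an adverse event would appear.
- An anomaly involving death, hospitalization or disability could meet a listed SAE criterion.
- Staff stay in contact with health care providers, and the DSMB includes an obstetrics specialist and sets its own monitoring.

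This stands against a reading that a reader might infer: that no anomaly would be captured or appear in any table. The documents do not support that.

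A reader might also infer that omission from the SAE list blocks IRB reporting. It does not. The 7-day rule covers any adverse event that is unexpected and related, serious or not. A defect already named as a risk could be classed as expected and so miss that rule, but that turns on expectedness, not on SAE status.

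Nor can the documents show that the regulatory citation is wrong or that other SAE criteria, such as life-threatening events, are missing. They do not reproduce the regulation, and no conflict within them bears on either.

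What the reply does not supply is assurance. The text never says that infant events count as adverse events or SAEs. SAP 8.1 uses participants as the denominator. Adverse-event collection often ends before delivery, and the review that does reach delivery has no anomaly item in the SAP.

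**Conclusion.** The point holds as a gap in assurance. A named fetal risk is absent from the SAE definition and from the SAP's birth outcomes. For early enrollees, adverse-event collection normally ends before birth. Nothing in the documents ensures that an anomaly found at delivery is captured, notified to the site PIs within 24 hours, included in the SAE reports to the funder and sponsor, or tabulated by arm.

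If the background risk is 2-5%, at least one such birth among the 106 women is likely, so staff would probably need a rule that the plan does not give. These counts say nothing about an effect of the VLNC cigarettes, and a trial of this size could not be expected to show one. The conclusion does not depend on the assumed rate. It rests on the text and, for timing, on delivery at about 37 to 41 weeks. The primary analysis is not affected.

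**What to change.** 1. **SAP 6.4:** add congenital anomaly as a birth outcome, abstracted from the birth records already under review and reported descriptively by arm. No test is needed.
2. **Protocol, Adverse Events:** add congenital anomaly in the offspring to the SAE list. State that infant events count and that they are collected through the birth-record review, so that collection does not stop at the last study contact.
3. **Protocol, Birth Outcomes Data:** name the abstracted variables so that they match SAP 6.4.

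The cost is one more abstraction item and a few more SAE reports. Sample size, visits and inference do not change. Two limits remain. The fix works only if maternal birth records document anomalies, which the documents do not show. It also leaves the 7-day IRB rule as it is, since that rule depends on whether the event is judged unexpected and related.

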The Primary Aim of Study 2 is to compare the effects of cigarettes varying in nicotine yield on smoking rate. The primary endpoint is cigarettes per day (CPD) at 12 weeks. CPD will be collected by daily IVR and/or TLFB at each session to assess cigarette use in the days since the last interview. This will yield a continuous record of cigarette use throughout the study. A weekly average will be obtained for analysis by averaging CPD from the previous visit to the current visit. Additional measures addressing this aim are breath CO level, urinary cotinine concentration, and nicotine dependence (FTND, WISDM) scores. Secondary Aim 1 is to assess adherence to assigned tobacco products and use of multiple nicotine

products during extended exposure. Secondary Aim 2 is to quantify the effects of VLNC cigarettes on (a) biomarkers of exposure to tobacco carcinogens (urine total cotinine, NNAL, PAH)s.

To examine these Aims, repeated measures analysis of variance (ANOVA) will be used for outcomes that are measured repeatedly from baseline to the end of the treatment phase. Each repeated measures ANOVA model consists of five terms: cigarette condition effect, visit effect, interaction effect between cigarette condition and visit, random subject effect (between-subject error), and random error (within-subject error). The variance-covariance structure will be specified as the first-order autoregressive, and variance parameters will be estimated using restricted maximum likelihood method with the Satterthwaite approximation. First, the VLNC condition will be compared to the usual brand condition; if significant differences are observed ($p < 0.05$), the simple effects of visit will be examined within the VLNC condition and the usual brand condition. Biomarkers will be analyzed on natural log scales so that ANOVA model assumptions of normality and equal variances hold. Geometric means in original units will be calculated as well. Interaction terms between BMI and cigarette condition will be added to these models to explore possible moderating effects of obesity on the relationship between cigarette condition and biomarkers. Differences between groups in self-reported quit and cigarette reduction rates at the 4-week post-treatment follow-up period will be evaluated using Chi-square tests, as will be the case for other discrete outcomes such as drop-out rates. SAS (SAS Institute Inc., USA) will be used for most analyses, but may be supplemented by use of STATA or R.

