To help protect the participant's privacy, [name], PhD, has received a Certificate of Confidentiality from the National Institutes of Health. With this certificate, the researchers cannot be forced to disclose information that may identify the participants, even by a court subpoena, in any federal, state, or local civil, criminal, administrative, legislative, or other proceedings. The researchers will use the Certificate to resist any demands for information that would identify the participants, except as explained below. The Certificate cannot be used to resist a demand for information from personnel of the United States Government that is used for auditing or evaluation of federally funded projects or for information that must be disclosed in order to meet the requirements of the Federal Food and Drug Administration (FDA).

The Certificate of Confidentiality does not prevent the participant or a member of their family from voluntarily releasing information about themselves and their involvement in the research. If an insurer, employer or other person obtains the participant's written consent to receive research information, then the researcher may not use the Certificate to withhold that information.

The Certificate of Confidentiality does not prevent the researchers from disclosing voluntarily, without consent, information that would identify the individual as a participant of the research project in instances such as evidence of child abuse or a participant's threatened violence to self or others.

Outcome Variables

Primary Endpoints for Study 1:

- 1) Nicotine withdrawal (i.e., MNWS)
- 2) Rank ordering of ability of each nicotine cigarette dose to substitute for usual brand dose cigarette

3) Establish cross-price elasticity for each nicotine dose

Primary Endpoints for Study 2:

- d. Number of cigarettes smoked per day: study cigarettes, combined study and non-study cigarettes
- e. Measure of exposure (i.e., urinary cotinine, expired breath CO, nicotine dependence)

Secondary Endpoints for Studies 1 and 2:

- 1) Measures of adherence: non-study cigarette use, drop-out rate
- 2) Measures of psychiatric symptoms: BDI, OASIS
- 3) Measures of discomfort/dysfunction: MNWS, QSU-brief
- 4) Measures of other health-related behaviors: weight (Study 1 only)
- 5) Measures of nicotine/tobacco dependence: FTND, WISDM-brief
- 6) Measures of tobacco exposure: CO, total nicotine equivalents, NNN, NNAL, minor alkaloids

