### **5.2. Per-Protocol Population**

A separate per-protocol population will also be used for this study, with the results from these analyses compared to those of the full analysis population in order to examine whether missing data affects the outcomes of interest. Participants who complete the 12-week protocol will represent the per-protocol population.

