## **7. Statistical Analysis**

### **7.1. General Approach**

To examine these Aims, repeated measures analysis of variance (ANOVA) will be used for outcomes that are measured on multiple occasions from baseline to the end of the intervention phase. Each repeated measures ANOVA model consists of five terms: cigarette condition, visit, interaction between cigarette condition and visit, a random effect for study site, a random participant effect (between-subject error), as well as random error (within-subject error). Variance parameters will be estimated using restricted maximum likelihood method with the Satterthwaite approximation. In the event of a statistically significant condition effect or a condition-by-visit interaction, post-hoc tests will be conducted in order to explore the nature of the significant findings.

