## **7.3. Primary Endpoint Analysis**

### **7.3.1. Primary Analysis**

The primary endpoint is CPD during Week 12, compared to the CPD at baseline. While the primary outcome is the mean total CPD, consisting of both study and non-study cigarettes, the analyses will be repeated examining only the CPD contributed by study cigarettes. CPD will be computed as the mean CPD calculated on a weekly basis. Data analysis will use repeated measures analysis of variance, with two conditions and two time points (baseline and Week 12). In addition, the analysis model will include a random effect for site, a random

participant effect and random error (within-subject error). Variance parameters will be estimated using restricted maximum likelihood method with the Satterthwaite approximation.

Because CPD will be measured weekly, additional analyses will be performed including data collected at all time points. The analysis will be conducted in a manner similar to that described above, with the exception that there will be 13 time points: baseline and Weeks 1 through 12. For these analyses, the variance-covariance structure will be specified as first-order autoregressive.

Additional outcomes include the CPT, breath CO level, urinary cotinine concentration, and nicotine dependence and withdrawal scores. These will be examined in a manner similar to that described above for CPD. Natural log transformations will be performed as needed so that ANOVA model assumptions of normality and equal variances hold. Geometric means in original units will be calculated as well. Note that not all outcomes are assessed at weekly in-person visits. The time points at which each outcome is assessed is described in Section 6.

Finally, several assessments will be made at baseline as well as at the abstinence visit, which occurs the day following the Week 12 assessment. At this visit, measures of craving and withdrawal will be completed. The analysis will be similar to that described above for the CPD comparing baseline CPD to that reported at the end of the trial. The analysis will deviate from that described only in the timing of the tasks, with the time points consisting of the baseline and the abstinence visits, rather than the baseline and Week 12 visits reported above.

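### The carbon monoxide rule ends follow-up as well as product use, so a Study 2 trigger before Week 12 leaves the Week 12 outcome by assignment unobserved

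*Protocol*

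**What the plan says.** The lead-in to the mandatory list in the protocol section Withdrawal or Monitoring of Participants reads "participants will be withdrawn immediately from the study if any of the following occur". Item 6 repeats the scope: "A participant will be withdrawn from the study if the average of two consecutive CO readings during the same visit is more than double" the Baseline measurement. Its second limb is any reading above 50 ppm. The list that follows it, by contrast, leaves withdrawal to the investigator or medical professional. Neither document describes daily telephone reports (IVR), visits or urine samples after such a withdrawal.

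The primary endpoint in SAP 6.1 and 7.3.1 is CPD in Week 12. On the model, SAP 7.3.1 says: "Data analysis will use repeated measures analysis of variance, with two conditions and two time points (baseline and Week 12"). It then plans a second model with 13 time points: "additional analyses will be performed including data collected at all time points".

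Breath CO and urinary cotinine serve the same aim. The protocol's Outcome Variables section lists "Measure of exposure (i.e., urinary cotinine, expired breath CO, nicotine dependence") under the Study 2 primary endpoints. SAP 6.1 and 7.3.1 treat them as additional measures, analysed in a similar way to CPD.

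SAP 5.1 analyses women by assigned condition whatever their compliance. SAP 5.2 adds a completer set: "Participants who complete the 12-week protocol will represent the per-protocol population". The missing-data section of the SAP relies on maximum likelihood under missing at random, with last observation carried forward (LOCF) and multiple imputation as sensitivity analyses.

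**The concern.** The rule acts on a measurement taken after randomization, and that measurement belongs to the primary aim. A woman who trips it at any of Weeks 1 to 11 contributes baseline CPD but no Week 12 CPD. The two-time-point CPD model does not contain the CO reading that caused the gap. Missing at random is therefore doubtful in that model, unless the trigger is unrelated to Week 12 CPD once baseline CPD is known. If triggers are unequal between arms and the women affected smoke more than the rest, the arm that loses more of them looks better than it is.

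The completer set in SAP 5.2 leaves out the same women, so comparing it with the full analysis cannot show what their absence does. The rule also works against SAP 5.1: an analysis by assignment regardless of compliance needs the Week 12 value of a woman who has stopped her product, and the protocol stops collecting it.

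**Working it through.** **Numbers per arm.** The plan has 90 completers, 15% attrition and 5 pilot participants (protocol, Study 2 Recruitment). 90/0.85 = 105.9, rounded up to 106; 106 + 5 = 111, which reproduces the stated enrolment. 106/2 = 53 per arm. Planned attrition is about 0.15 × 53 = 8 women per arm.

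**Planning values.** Pregnant women smoked 12.1 CPD, and the expected difference is 5 CPD (SAP 4.2), so VLNC is put at 12.1 − 5 = 7.1. No SD is stated. Solving 80% power with 45 per arm at two-sided 0.05 (sidedness assumed) gives SD = 5/[(1.960 + 0.842) × √(2/45)] = 8.47.

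**Not in the documents.** The trigger rate, the within-woman variability of CO and its link to CPD are not given. All are assumed below.

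**Illustration 1: CO falls 25% on VLNC.** The 25% comes from a trial in another population, cited in the protocol's background; usual brand is taken as unchanged. Assumptions: participant SD of log CO 0.5; within-woman SD 0.2 to 0.3 with weekly autocorrelation 0.5 or 0.8; CPD participant SD 4 and within SD 3, correlated 0.5 with log CO; withdrawal at the first visit above twice the mean of two baseline readings. The 50 ppm limb is not simulated.

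- In the settings within planned attrition, usual brand loses 1 to 6 of 53 women and VLNC 0 to 1.
- The two-time-point model gives CPD differences of 4.84 to 4.96 against a true 4.99 to 5.02, an understatement of 0.04 to 0.18. A repeat run gave 4.82 to 4.95.
- The 13-time-point model is within 0.01 of the truth. LOCF gives 5.01 to 5.25, erring the other way.
- If CO and CPD are not linked within a woman, the CPD bias is 0.00.

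**Check under different assumptions.** This uses SD 8.47, a baseline to Week 12 correlation of 0.6, median CO 15 ppm and both limbs of the rule.

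- CO down 25%, within-woman SD 0.15 or 0.20: 2.6% or 5.3% of usual-brand women and 0.6% or 1.0% of VLNC women are withdrawn; the effect shrinks by 0.04 or 0.17 CPD. At SD 0.3, 21% of usual-brand women would be withdrawn, beyond the 15% allowance, and the shrinkage is 0.87.
- CO equal in both arms: bias within 0.1 CPD.
- CO up 25% on VLNC, SD 0.15: 2.7% v 9.9% are withdrawn and the effect is overstated by 0.34 CPD.

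The sign changes with the assumed effect of VLNC on CO.

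**Illustration 2: some VLNC women compensate.** Suppose 4 VLNC women and no usual-brand women are withdrawn, all smoking 20 CPD. With no credit for baseline CPD, the overstatement is 4 × (20 − 7.1)/53 = 0.97. With a participant effect holding half the variance and a baseline of 14 CPD, it is 4 × [12.9 − 0.5 × (14 − 12.1)]/53 = 0.90; with a baseline of 20 CPD, it is 4 × [12.9 − 0.5 × (20 − 12.1)]/53 = 0.68. The 13-time-point model leaves 0.12 to 0.78. If the women would have stayed at 20 CPD, LOCF leaves about 0.

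**What continued follow-up would show.** In the same 4 v 0 case, the difference by assignment is 5.0 − 4 × (c − 7.1)/53, where c is the women's CPD off product. It is 4.03, 4.62 or 5.54 for c = 20, 12.1 or 0. No analysis of the data now planned can tell these apart.

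**The case against.** The strongest reply is that the SAP already answers the gap. The woman stays in the full analysis population and her baseline is used. Both documents specify a participant effect (SAP 7.1: "a random participant effect (between-subject error), as well as random error (within-subject error"). The 13-time-point model keeps her earlier weeks, and LOCF and multiple imputation, by condition if needed, test robustness. In Illustration 1 the two-time-point and LOCF results bracket the truth; in Illustration 2, LOCF removes the bias if smoking stays at 20 CPD. This stands as mitigation. It does not close the point: none of the CPD analyses is stated to use the triggering CO reading, and none observes what happens by assignment after product stops.

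It is also fair that quitters, whom the protocol keeps in follow-up, are not safety withdrawals. The precedent shows only that follow-up without product is workable here.

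Four stronger readings are tempting and not supported:

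- A reader might infer that the woman drops out of the analysis altogether. SAP 5.1 keeps her in.
- A reader might infer that CO and urine belong to the primary two-time-point analysis. SAP 6.1 and 7.3.1 make them additional measures, although the protocol's outcome list groups CO with the primary endpoints.
- A reader might take 0.97 CPD as the expected bias, in favour of VLNC. It rests on no documented rate and gives no credit for baseline CPD. The protocol's background reports no compensation, or only a short-lived one, with VLNC.
- A reader might see the unspecified Baseline in item 6 as a serious gap. Study 2 Statistical Methods already averages the baseline visits, so this is a matter of detail.

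**Conclusion.** The point holds as a cheap improvement. The rule mandates withdrawal from the study on a post-randomization CO value, outcome collection then ends, and the Week 12 value that SAP 5.1 needs is not observed. Because no trigger rate is documented, neither direction nor size can be stated as fact. In the one case tied to a CO effect cited in the protocol, a 25% fall on VLNC, the CPD bias is about 0.04 to 0.2 of 5 CPD, against VLNC, and the additional 13-time-point model removes it. That rests on the assumed CO variability and on withdrawals within planned attrition. If some VLNC women compensate, the bias would favour VLNC; the larger figures for that case are illustrations only. Nothing here questions the threshold or the safety reason for stopping product.

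**What to change.** For Study 2, keep the CO threshold and the immediate stop of study cigarettes. In item 6, replace withdrawal from the study with wording such as: *study product is stopped; unless she withdraws consent, the participant continues daily IVR reports, weekly CO and the remaining Week 6 and Week 12 urine samples, and these data stay in the full analysis set.* Mirror this in SAP 5.1.

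The cost is the wording plus visits already planned for the few women affected. For a stop at Week 1, visit payments are at most 9 × $100 + 2 × $150 = $1,200 per woman, plus IVR payments and bonuses already on offer. The downside is that Week 12 data for these women are off-product. They support the estimate by assignment and do not show the effect of continued product use, which the SAP should say.
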